## 10. STATISTICS AND DATA ANALYSIS

### 10.1. Sample Size Calculation

Phase 1: Regression model.

A detailed search of the literature found no data upon which a sample size calculation could be based. However, "rules of thumb" have been established for regression models for which sample size calculations cannot be calculated. The accuracy of several of these estimations has been assessed by Green [14] and, based on his research the following estimate method was selected:

$$S = 104 + i$$

Where S = Sample size; I = Number of independent variables (i.e. the number of variables we will use to predict the tissue volume). This is assuming the treatment effect would be moderate. Taking into account the number of variables this results in a sample size of 110.

Phase 2: Comparison of accuracy using limits of agreement analysis.

The sample size of 246 samples was calculated based on the precision of 95% confidence limits for 95% limits of agreement using the formulae taken from Bland and Altman [15]. The precision for the limits of agreement confidence interval was set at 5% as a difference of more than 5% could affect the accuracy of the boost radiotherapy in the CI's clinical judgement. The standard deviation of the differences using the current method was estimated at 23.26%, based on a clinical audit carried out by the CI between January and December 2022.

### 10.2. Planned Recruitment Rate

The study set-up will require 4 months. Based on our Unit's number of treated cancers (>800/year of which at least 60% are WLE), the estimated time to recruit enough patients to complete phase 1 of the study would be 4 months. the recruitment time for phase would require another 9 months. There will be no recruitment gap between phase 1 and phase 2 as the analysis of the data from phase 1 will be carried out simultaneously to phase 2 recruitment. Finally, we will require 4 months

for data analysis and study close-out. The results of this research will be presented in breast cancer conferences and published in a peer-reviewed journal.

### **10.3. Statistical Analysis**

#### **10.3.1. Summary of Baseline Data and Flow of Patients**

The baseline variables (age and BMI) will be reported with medians & Interquartile Ranges (IQR).

A Consolidated Standards of Reporting Trials (CONSORT) flow diagram will not be required for this study.

#### **10.3.2. Outcome Analysis**

Study phase 1 primary outcome: A regression model to estimate the tissue volumes.

This phase will include the 6 explanatory / independent variables:

1. The diameter of the mass (mm)
2. The healthy tissue density (using a Visual Analogue Scale (VAS))
3. The area occupied by the tumour (% of tissue sample)
4. Specimen weight (g)
5. Patient age
6. Patient BMI

The outcome / dependent variable will be the tissue volume, measured using the water displacement / Archimedes principle.

The regression model will be fitted using a bi-directional stepwise regression. Variables will be included if they make an important improvement in the model's fit. They will be excluded if, after other variables have been included in the model, they no longer make an important improvement in the model's fit. The model will stop fitting variables when both of the following conditions are met:

1. None of the variables that are not already included will make an important difference to the model's fit if they are included.
2. All of the variables that are included do make an important difference, so none of them should be removed.

The definition of "important" improvements in the model's fit and how they will be assessed will be described in detail in the Statistical Analysis Plan.

Study phase 2: Assessing the accuracy of the model obtained from phase 1.

This phase of the study will use a second collection of tissue samples, that have not been used to develop the model. It is needed because the regression model has been developed to predict the tissue volumes of the first sample as accurately as possible. It may not estimate other patients' volumes as accurately as these patients and we need to demonstrate that, even if the estimates for

other patients are less accurate than for the original sample of patients, they are still more accurate than the current method.

Study phase 2 primary outcome: Comparison of the new regression-based method and the current method with the gold standard measurement (using the Archimedes/water-based method). The estimates will be compared to the measured tissue volumes using two limits of agreement analyses (Bland and Altman [15]).

Study phase 2 secondary outcome 1: The differences between the two estimation methods and the gold standard tissue volumes will be compared using intraclass correlation. This will demonstrate how strongly related the two estimation methods are to each other. This is not a within-patient comparison but a comparison closely the results from the new estimation methods resemble the results from the current method.

Study phase 2 secondary outcome 2: The differences between the two estimation methods and the gold standard will be compared within-patient using a paired t-test. The mean difference in accuracy and its standard deviation will be reported.

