**STUDY SUMMARY**

Study Title:	DEVELOPMENT OF A NEW APPROACH TO MEASURE THE VOLUME OF BREAST TISSUE REMOVED DURING WIDE LOCAL EXCISION USING SPECIMEN WEIGHT AND MAMMOGRAPHIC DENSITY
Local Study Reference:	UHDB/2019/088
Study Design:	Single-centre proof-of concept study
Study Participants:	Women undergoing breast conserving surgery for breast cancer as standard care.
Planner Number of Sites:	1
Planned Sample Size:	Phase 1: 110; Phase 2: 246
Treatment Duration:	n/a
Follow Up Duration:	n/a
Planned Start Date:	01/09/2023
Planned Recruitment End Date:	31/10/2024
Planned Study End Date:	30/11/2024
Research Question/ Aims:	The objective of this research project is to evaluate a novel method of obtaining simple and accurate estimates of the volume of breast tissue excised during breast conserving surgery by putting the weight of the surgical specimen in relation with its radiological density. The primary endpoint is to establish whether the method is superior to the currently used method.

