### 2. RATIONALE

The aim of this study is to evaluate a novel method of obtaining simple and accurate estimates of the volume of a WLE specimen by putting the specimen weight in relation with its radiological density.

In women with smaller breasts and larger tumours oncoplastic breast surgery techniques such as volume replacement with chest wall perforator flaps (CWPF) can be used to enable breast conservation and avoid deformity. In CWPF, the surgical cavity resulting from WLE is filled volume-for-volume with non-breast tissue (skin and fat) harvested from the surrounding chest wall.

A previous research study demonstrated how, in the context of CWPF volume replacement, the standard approach for tumour bed contouring (based solely on the metal clips placed by the surgeon) is not accurate (contoured volume significantly smaller than specimen volume). A new method of contouring has been proposed including the clips and the typical appearance of the flap in the planning CT scan [7,8].

On average, the tumour bed volume obtained with this method closely matched the estimated surgical specimen volume obtained from its weight (only 1.02 ml smaller on average). However, the variability between the individual cases was high (SD 43.6). This is thought to be related with the difference in breast density between the patients leading to a non-accurate estimate of the specimen volume based on its weight [8].

In the context of volume replacement surgery, having an accurate estimate of the volume of breast tissue removed with surgery could help to increase the accuracy of tumour bed contouring. If the boost volume is underestimated, then the target penumbral breast tissue will be missed (only the central portion of non-breast flap tissue would be irradiated) potentially leading to higher rates of local recurrence. If the boost volume is overestimated, then an excess dose of radiation would be administered with negative impact on the final cosmetic outcome (increased fibrosis and loss of volume).

During a meeting with a group of breast cancer patients held during the design phase of this study, the importance of accurate radiotherapy planning has been unanimously acknowledged by all participants. In fact, both under- and overestimation of the boost target volume (and subsequent increased risk of local recurrence or impaired cosmetic outcome respectively) could have negative impact on patients' quality of life and require further treatment including surgery.

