### 3. OBJECTIVES AND OUTCOME MEASURES/ ENDPOINTS

#### 3.1. Objectives

**Phase 1:** To develop a regression model to estimate tissue sample volume using a combination of explanatory variables potentially including specimen weight, radiological density, patient's age, patient's BMI, tumour histology and grade.

**Phase 2:** To compare the estimates of volume derived from the regression model identified in phase 1 and then the currently used estimation method (dividing the sample weight by the approximate density of 0.958g/ml to determine which method produces the most accurate estimates.

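### Phase 1 stepwise selection is free to remove radiological density, the variable that defines the novel method, and Phase 2 would then test a model without it

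*Protocol*

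**What the plan says.** The Study Summary describes the method as obtaining volume estimates "by putting the weight of the surgical specimen in relation with its radiological density", and Section 2 repeats the definition. Section 4 names VAS assessment of the excised specimen's density as what is new about the study.

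The Phase 1 objective in Section 3.1 is looser: "To develop a regression model to estimate tissue sample volume using a combination of explanatory variables potentially including specimen weight, radiological density", followed by age, BMI, histology and grade. Section 10.3.2 then says "This phase will include the 6 explanatory / independent variables": mass diameter, healthy-tissue VAS density, percentage of the sample occupied by tumour, specimen weight, age and BMI. On fitting it says "The regression model will be fitted using a bi-directional stepwise regression". On removal of variables it says "They will be excluded if, after other variables have been included in the model, they no longer make an important improvement in the model's fit".

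No variable is exempt. The threshold is deferred: "The definition of 'important' improvements in the model's fit and how they will be assessed will be described in detail in the Statistical Analysis Plan". Sections 3.1 and 10.3.2 carry the model identified in Phase 1 into Phase 2, where it and the 0.958 g/ml rule are each compared with water displacement. The protocol does not say what follows if density is not selected.

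**The concern.** The study's premise is that specimen-specific radiological density makes weight a better guide to volume. The analysis leaves a data-driven rule, applied to 110 specimens, to decide whether density appears in the equation at all. Only the meaning of an important improvement is left to the SAP. That every candidate, density included, may be removed is already fixed in the protocol.

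If VAS density is removed, a favourable Phase 2 result could come from recalibrating weight or from the other covariates, and could be wrongly credited to density. An unfavourable result would say nothing about density. With a weak signal, failing a selection threshold is poor evidence of no effect. Section 10.2 plans no gap between the phases, so Phase 2 specimens would be accruing before the outcome of selection is known.

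There is a smaller harm in the other direction. If the signal is weak and VAS happens to pass the threshold, its coefficient tends to be too large, and that coefficient goes forward to Phase 2.

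**Working it through.** **Inputs from the protocol.** Phase 1 n = 110, Phase 2 n = 246, precision 5%, and SD of the current method's differences 23.26% (Section 10.1). Fat 0.92 g/ml, fibro-glandular tissue 1 g/ml, conventional density 0.958 g/ml (Section 1). Six candidates (Section 10.3.2).

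**Assumptions, not in the protocol.** VAS SD of 20, 25 or 30 points (a uniform 0-100 spread has SD 29). Selection threshold: p<0.05, AIC (about p<0.157) or adjusted R² (about p<0.32). Residual SD in Phase 1: 23.26%, 10% or 5%. Density linear in VAS, and VAS unrelated to the other candidates.

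**The plan's own figures reproduce.** Phase 1: 104 + 6 = 110. Phase 2: the half-width of the confidence interval for a limit of agreement is t(0.975, n−1) × SD × √(1/n + 1.96²/(2(n−1))). At n = 246 this is 1.9697 × 23.26 × √(1/246 + 3.8416/490) = 5.00 (4.999). At n = 245 it is 5.01. So 246 is the smallest n that meets 5%.

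**Size of the density signal.** With V = W/(0.92 + 0.08 × VAS/100), dividing by 0.958 misstates volume by 0.92/0.958 − 1 = −4.0% for pure fat and by 1/0.958 − 1 = +4.4% for pure gland. The SD of the density effect is about 8% × (VAS SD/100)/0.96, which is 1.67%, 2.08% and 2.50% for VAS SDs of 20, 25 and 30. Against a residual SD of 23.26%, partial R² = effect²/(effect² + 23.26²) = 0.005, 0.008 and 0.011.

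**Chance that VAS is dropped.** This is one minus the power of the partial F test with 1 and 110 − 6 − 1 = 103 degrees of freedom and noncentrality 110 × effect²/residual². For example, with VAS SD 25 and residual SD 23.26%, the noncentrality is 110 × 2.08²/23.26² = 0.88. The critical F at p<0.05 is 3.93, and the chance of falling below it is 85%.

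| Residual SD | Threshold | VAS SD 20 | 25 | 30 |
|---|---|---|---|---|
| 23.26% | p<0.05 | 88% | 85% | 80% |
| 23.26% | AIC | 73% | 68% | 61% |
| 23.26% | adjusted R² | 56% | 50% | 43% |
| 10% | p<0.05 | 59% | 42% | 26% |
| 10% | AIC | 37% | 22% | 12% |
| 5% | p<0.05 | 7% | 1% | <1% |
| 5% | AIC | 2% | <1% | <1% |

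Simulating the full bi-directional procedure with six candidates (1000 runs per setting, residual SD 23.26%) gave similar or slightly higher drop rates: 87-92% at p<0.05, 72-78% under AIC and 91-94% under BIC. The even-odds point lies at a residual SD of about 9-13% for p<0.05 and 12-19% for AIC.

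**Inflation when selected.** In simulations at 23.26%, when VAS passed the threshold its mean coefficient was roughly 2.2 to 2.9 times the average over all runs, depending on the threshold.

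**The case against.** Four points deserve weight.

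*The 23.26% is not a Phase 1 residual.* It is the audit SD of the current method's differences, used to size Phase 2. Section 2 attributes a wide spread in an earlier study to density differences, which would make the residual smaller. This stands as a limit on the probabilities. The protocol's own tissue densities, however, cap the density effect at about 4% either way, so density alone cannot account for much of a 23% spread. What else the Phase 1 residual will contain is unknown.

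*The threshold is left to the SAP.* A reader might infer that the plan would usually drop density. The documents do not support that as a general statement: under adjusted R² the chance is near even at 23.26%, and at 10% or below the result largely reverses.

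*Forcing density in buys little accuracy if the noise is really 23%.* This stands. Simulating both phases at that error level gave a Phase 2 difference SD of 17.60 ml with VAS dropped and 17.61 ml with it forced in. The reason to force it in is that the comparison then means what the study says it means.

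*Phase 2 would still have an answer.* A reader might infer that Phase 2 could not meet its objective. It could: Section 3.2 asks for a model that predicts as accurately as possible, and whether the selected model beats 0.958 remains testable. Tumour percentage and mass diameter, also read from the specimen x-ray, might stay in. What is lost is the specific question about VAS density. Section 9.2 lists VAS without limiting it to Phase 1, so a density model could be examined in Phase 2 later, but nothing in the protocol plans for that.

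**Conclusion.** The point holds as a structural inconsistency. The stated method depends on radiological density, the fixed selection rule can remove it, and no consequence is specified. This is true at any error level.

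The probability is conditional. With a residual SD near 23.26%, densities of 0.92 to 1.00 g/ml and a VAS SD of 20 to 30 points, VAS is dropped in 80-88% of samples at p<0.05, 61-73% under AIC and 43-56% under adjusted R². At a residual SD of 10% it is kept in 41-74% at p<0.05 and 63-88% under AIC; at 5% it is kept in 93% or more. The residual SD, the VAS spread and the threshold are all assumptions. The change is worth making, but the point does not show that the study would fail.

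**What to change.** In Section 10.3.2, state that specimen weight and healthy-tissue VAS density are always in the Phase 1 equation, and that stepwise selection applies only to mass diameter, tumour percentage, age and BMI. Align the Phase 1 objective in Section 3.1, so that weight and density are no longer only potential components.

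The cost is a sentence or two and about one degree of freedom out of about 100, with no new data and no extra patients. The return is that Phase 2 evaluates the method the protocol describes, with a density coefficient that has not been inflated by being selected. It does not promise better accuracy, and the gain would be negligible if the residual SD is really about 23%.

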#### 3.2. Outcomes

**Phase 1 primary outcome:** A regression model using a combination of variables from specimen weight, radiological density, patient's age, patient's BMI, tumour histology and grade that predicts surgical specimen volume as accurately as possible.

**Phase 1 secondary outcomes:** not applicable.

**Phase 2 primary outcome:** The 95% limits of agreement (Bland and Altman [15]) with 95% confidence limits of the novel method using the regression model and the current method (dividing the specimen weights by 0.958, regardless of their radiological density) against the gold standard measurement of specimen volume (the water displacement / Archimedes method).

**Phase 2 secondary outcome 1:** The Intraclass correlation (ICC) of the estimates using the new method and the current method. This will indicate how strongly the two methods resemble each other.

**Phase 2 secondary outcome 2:** A within-patient comparison of the new method and the current method using a paired t-test.

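### Phase 2 secondary outcome 1 has two conflicting inputs: section 3.2 puts the two methods' volume estimates into the ICC, while section 10.3.2 puts in their differences from the gold standard

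*Protocol*

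**What the plan says.** Protocol section 3.2 (Outcomes) defines Phase 2 secondary outcome 1 as "The Intraclass correlation (ICC) of the estimates using the new method and the current method" and gives its purpose: "This will indicate how strongly the two methods resemble each other". The gold standard plays no part.

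Protocol section 10.3.2 (Outcome Analysis) opens its paragraph on the same outcome with "The differences between the two estimation methods and the gold standard tissue volumes will be compared using intraclass correlation". Here the inputs are the two errors, new minus gold standard and current minus gold standard. The second sentence states the purpose: "This will demonstrate how strongly related the two estimation methods are to each other". The third adds: "This is not a within-patient comparison but a comparison closely the results from the new estimation methods resemble the results from the current method".

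The next paragraph, on secondary outcome 2, begins almost identically: "The differences between the two estimation methods and the gold standard will be compared within-patient using a paired t-test".

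The one matter that section 10.3.2 expressly leaves to the statistical analysis plan is what counts as an important improvement in model fit. The input to the ICC is not deferred. It is stated twice, in two ways.

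**The concern.** An ICC compares variation between specimens with disagreement within specimens. If the inputs are volume estimates, the between-specimen variation is mainly specimen size. The current estimate is weight divided by 0.958, and weight is a candidate predictor for the new one, so this ICC is expected to be high. If the inputs are errors, specimen size has been subtracted and what remains is the error that the two methods share.

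The error ICC therefore does not answer the question both sections ask. Two methods whose estimates almost coincide can have a low error ICC when the remaining errors are small. A large error common to both, such as measurement error in the water-displacement volume, pushes it towards 1. An analyst who follows the opening sentence of section 10.3.2 literally would report a quantity that is neither the outcome defined in section 3.2 nor a measure of the stated purpose.

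**Working it through.** **Inputs from the protocol.** Section 10.1: "The standard deviation of the differences using the current method was estimated at 23.26" per cent; "The precision for the limits of agreement confidence interval was set at 5" per cent; n = 246. Sections 3.2 and 4: current estimate = weight / 0.958. Section 1: fat 0.92 g/ml, fibro-glandular tissue 1.00 g/ml. The protocol gives no weight distribution, no error SD for the new method and no correlation between the two methods' errors. Those are assumed below and shown as ranges.

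**The plan's own figure.** The protocol states no ICC value, so the only related figure to reproduce is the sample size. The half-width of the confidence interval for a limit of agreement is t(0.975, n−1) × s × √(1/n + 1.96²/(2(n−1))). With s = 23.26 this is 5.009 at n = 245 and 4.999 at n = 246, so 246 is reproduced. It does not depend on the ICC.

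**Algebra.** Let C be the current estimate, M the new estimate and V the gold standard. Then (C − V) − (M − V) = C − M. Within-specimen disagreement is identical under both definitions; only the between-specimen part changes.

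**A simple model.** Let V = C(1 + g + e) and M = C(1 + g), with g and e independent with mean zero, and C independent of both. Here g is what the new method corrects and e is what is left. Put SD(g + e) = s = 0.2326 and SD(e) = k·s. With equal means, the large-sample ICC is 2·cov/(sum of the two variances).

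- Errors: C − V = −C(g + e) and M − V = −C·e, so ICC = 2k²/(1 + k²).
- Estimates: ICC = 2cv²/[2cv² + (1 + cv²)(1 − k²)s²], where cv is the coefficient of variation of specimen weight and s² = 0.0541.

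**Case closest to the documents: density alone.** With a uniform fat share between pure fat and pure gland, the density SD is 0.08/√12 = 0.0231 g/ml, or 0.0231/0.958 = 2.41%. Then k² = 1 − (2.41/23.26)² = 0.989 and k = 0.995.

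- Errors: 2(0.989)/1.989 = 0.995.
- Estimates: with (1 − k²)s² = 0.0241² = 0.00058, 0.998 at cv 0.4 and 0.999 at cv 0.7 and 1.0.

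The two definitions almost agree.

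**Assumed reductions in error SD, weight CV 0.4 to 1.0.**

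| New error SD / current error SD (k) | ICC of estimates | ICC of errors |
|---|---|---|
| 0.90 | 0.96 to 0.99 | 0.90 |
| 0.75 | 0.92 to 0.98 | 0.72 |
| 0.50 | 0.87 to 0.96 | 0.40 |

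For k = 0.5, (1 − k²)s² = 0.75 × 0.0541 = 0.0406. At cv 0.4 the estimate ICC is 0.32/(0.32 + 1.16 × 0.0406) = 0.87; at cv 1.0 it is 2/(2 + 2 × 0.0406) = 0.96. The error ICC is 2(0.25)/1.25 = 0.40. Simulated datasets of 246 specimens agree (error ICC 0.89, 0.72 and 0.40).

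**A different error model.** Here V has mean 60 ml and CV 0.3 to 0.7, the current error SD is 23.26%, the new error SD is 10% to 23.26%, and the correlation between the errors is 0 to 0.9. Over this grid the estimate ICC ran from 0.61 to 0.99 and the error ICC from about 0.00 to 0.90. The estimate ICC was the higher in every scenario, by about 0.06 to 0.91. At CV 0.5 and new SD 15%, the pairs were 0.84 and 0.00 (correlation 0) and 0.97 and 0.82 (correlation 0.9).

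**The case against.** The best defence is that this is one loosely worded sentence whose meaning can be recovered. The second and third sentences of the paragraph in section 10.3.2 speak of the two methods' relation to each other and of their results, which fits section 3.2. The opening probably echoes the paired t-test paragraph below it, where differences from the gold standard do belong. This stands as a guide to what was intended. It supports the view that the opening sentence is the error; it does not make that sentence correct. It is also the only sentence there that says what enters the ICC.

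The second defence concerns size. The figures with a wide gap rest on assumed error reductions that the protocol does not forecast, and the case built from its own density range and SD shows almost no gap. This also stands. Denser tumour tissue or the other predictors could widen the gap, but the documents do not say by how much.

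A reader might infer three stronger things, none of which the documents support:

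- *That the study's conclusion turns on this choice.* The protocol sets no ICC threshold or decision rule, and accuracy is judged by limits of agreement.
- *That the gap is widest when the new method works.* That holds in the simple model only. In the second model, uncorrelated errors give an error ICC near 0 even when the new method's error SD equals the current one (estimates 0.79 at CV 0.5).
- *That the protocol should also fix the form of the ICC.* That can be left to the statistical analysis plan.

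**Conclusion.** The inconsistency is real and lies in the current text: one numbered outcome, one stated purpose, two different inputs. Section 3.2 has the input that fits the purpose, and the opening sentence in section 10.3.2 does not.

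The numerical consequence is uncertain. It is negligible (about 0.999 against 0.995) if density of 0.92 to 1.00 g/ml is all that separates the methods and the error SD is 23.26%. It is large (0.87 to 0.96 against 0.40) under the assumption that the new method halves the error SD, with an assumed weight CV of 0.4 to 1.0. The effect is confined to a descriptive secondary outcome. The primary limits-of-agreement analysis and the sample size of 246 are untouched. It is worth correcting because the literal instruction yields the wrong quantity and the correction is trivial.

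**What to change.** In section 10.3.2, replace the opening sentence for Phase 2 secondary outcome 1 with: *The volume estimates from the new method and from the current method will be compared using intraclass correlation.* This matches section 3.2. Add one statement that this ICC describes resemblance between the two methods and not accuracy against the gold standard. Carry the same input into the statistical analysis plan, where the form of the ICC can be chosen.

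The cost is one reworded sentence and one added statement. No further data, patients or procedures are needed.

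### Phase 2 secondary outcome 2: a paired t-test on signed differences from the gold standard compares mean bias only, so it cannot show which method is more accurate

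*Protocol*

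**What the plan says.** The Study Summary states the aim as superiority: "The primary endpoint is to establish whether the method is superior to the currently used method". Section 3.1 gives the Phase 2 objective as comparing the two estimates "to determine which method produces the most accurate estimates". Section 10.3.2 adds that the new estimates need to be shown to be more accurate than the current method in specimens not used to build the model.

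The primary Phase 2 analysis is two limits-of-agreement analyses, one per method, each against water displacement. No test or interval for the contrast between the methods is stated there.

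Secondary outcome 2 supplies that contrast. Section 3.2 defines it as "A within-patient comparison of the new method and the current method using a paired t-test", without mentioning the gold standard. Section 10.3.2 says: "The differences between the two estimation methods and the gold standard will be compared within-patient using a paired t-test", and then: "The mean difference in accuracy and its standard deviation will be reported". Neither section says that the differences are absolute or squared.

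Secondary outcome 1 is an intraclass correlation. Section 3.2 defines it as "The Intraclass correlation (ICC) of the estimates using the new method and the current method". Section 10.3.2 says instead: "The differences between the two estimation methods and the gold standard tissue volumes will be compared using intraclass correlation". Both sections give its purpose as resemblance between the methods; in section 10.3.2: "This will demonstrate how strongly related the two estimation methods are to each other".

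**The concern.** A method is accurate when its estimates lie close to the true volume, and that depends on both bias and spread. A paired t-test on signed errors looks only at the difference in mean error. Over-estimates and under-estimates offset each other, and a method with scattered errors can have the same mean error as one with tight errors.

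Spread is the problem this study sets out to solve. Section 2 reports that, in earlier work, the contoured tumour bed was on average only 1.02 ml smaller than the specimen volume estimated from weight, but with an SD of 43.6. Section 10.1 puts the current method's SD of differences at 23.26%. If the new method works by reducing that scatter, the planned test is not built to see it. If the two methods merely differ in mean bias, the test may be reported as a difference in accuracy when there is none.

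**Working it through.** **Inputs.** From section 10.1: n = 246 for Phase 2, SD of the current method's differences 23.26%, target precision 5%. Assumptions of this check: normal errors in percentage points, two-sided 5% level, correlation between the two methods' errors of 0, 0.5 or 0.9, and 4,000 simulated trials per scenario.

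**The plan's own figure.** The half-width of the 95% CI for a limit of agreement is t × s × √(1/n + 1.96²/(2(n − 1))). With s = 23.26, n = 246 and t = 1.970 on 245 df this is 4.999, within the 5% target. The sample size is reproduced, and nothing below changes it.

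**Step 1: the identity.** Let N, C and G be the new estimate, the current estimate and the gold standard for one specimen. Then (N − G) − (C − G) = N − C. On one simulated dataset of 246 specimens, the paired t-test on differences from G and the paired t-test of N against C gave the same result: t = 0.19197, p = 0.84792, 245 df. The section 10.3.2 wording and the section 3.2 wording therefore describe one and the same test, and G plays no part in it.

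The cancellation is exact for differences in ml. If the differences are taken as a percentage of G, the contrast becomes (N − C)/G. The gold standard then survives only as a positive scale factor, and the test is still one of equal mean (percentage) bias.

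**Step 2: a more accurate method that the test does not see.** Let the new method's error SD be 23.26/2 = 11.63, with both methods unbiased. The mean of N − C is then 0, so the signed test's null hypothesis is true and it should reject in 5% of trials. Simulated: 4.7–5.3%.

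For a normal error with mean 0 the mean absolute error is SD × √(2/π) = 0.798 × SD. That is 18.56 points for the current method and 9.28 for the new one, a difference of 9.28. The SD of an absolute error is SD × √(1 − 2/π) = 0.603 × SD, that is 14.02 and 7.01. With independent errors the standard error of the paired difference is √(14.02² + 7.01²)/√246 = 1.00. The effect is about 9 standard errors. Simulated rejection by the absolute-error test: 100% at every correlation.

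**Step 3: equal accuracy that the test reports as a difference.** Let both SDs be 23.26 and the biases +5 and −5. The two absolute errors have identical distributions, so accuracy is equal. The mean of N − C is 10. Its SD is 23.26 × √(2(1 − r)), where r is the error correlation.

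| r | SD of N − C | Standard error (SD/√246) | 10/SE |
|---|---|---|---|
| 0 | 32.89 | 2.10 | 4.77 |
| 0.5 | 23.26 | 1.48 | 6.74 |
| 0.9 | 10.40 | 0.66 | 15.08 |

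Against a critical value of 1.970, power is 99.7% at r = 0 and essentially 100% above that. Simulated: 99.6–100%. The absolute-error test rejects in about 5%.

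**Step 4: the ICC.** The two sections name different inputs: the estimates in 3.2, the differences from G in 10.3.2. In simulation with an assumed SD of true volumes of 50, the halved-SD scenario gave an ICC on estimates of 0.879 at r = 0 and 0.928 at r = 0.5. On differences it was about 0 and 0.400. The two definitions are not interchangeable. Swapping which method is the better one left the values essentially unchanged (0.880 and 0.927; about 0 and 0.396), as expected of a symmetric measure.

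**The case against.** **The primary outcome already addresses accuracy.** This stands. The limits of agreement, with confidence limits, show each method's bias and spread against the same gold standard, and Phase 2 is sized for them alone. A method with half the error SD would have limits half as wide. A reader might infer that the study cannot assess accuracy at all; the protocol does not support that. What is missing is a valid paired contrast.

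**Absolute differences may have been meant.** The label on the result hints at this, and a statistical analysis plan that is not at hand might define it. But section 10.3.2 states differences without qualification, and section 3.2 describes a plain comparison of the two methods. The protocol defers the stepwise fitting criteria to the SAP; it does not defer this.

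**A difference in mean bias is a legitimate quantity.** Agreed, under that name. The fault is calling it a difference in accuracy.

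**The ICC might be thought to fail in the same way.** It does not. The protocol claims only resemblance for it. Under the 3.2 definition the gold standard is never used, and under the 10.3.2 definition it does not cancel. A reader might also expect the ICC to be close to 1 whichever method is better, but its value depends on the spread of volumes and on the error correlation, as Step 4 shows. What stands is that the two sections disagree and that a symmetric measure cannot rank the methods.

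**Conclusion.** The point holds for secondary outcome 2 as written. The test described is one of equal mean bias, and its result is misnamed. Under the assumptions listed, it rejects at about its nominal 5% when the new method halves the error SD, and in 99.6–100% of trials when two equally accurate methods have opposite biases of 5 points.

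The identity needs no assumption beyond signed differences in ml. The percentages rest on normal errors, the section 10.1 SD of 23.26%, and the chosen halving and 5-point biases, which are illustrations and not protocol figures. How often the test would reach significance in a case where the new method is actually worse depends on an error correlation that the protocol does not give, so no figure is offered for that.

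This is a secondary outcome in a proof-of-concept study whose primary analysis is unaffected. It should be fixed, because it is the only stated between-method test for the superiority aim, but it is not fatal. The ICC mismatch is a lesser point of consistency.

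**What to change.** In sections 3.2 and 10.3.2, define secondary outcome 2 as follows. For each specimen compute the absolute percentage error of each method, |estimate − gold|/gold. Report the paired mean difference (new minus current) with a 95% CI, by bootstrap because absolute errors are skewed. If new − current is kept, report it as a difference in mean bias and label it so.

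For secondary outcome 1, choose one input, state it identically in both sections, describe it as a measure of resemblance, and say that it will not be used to rank the methods. The remark that it is not a within-patient comparison should be reworded, since both values come from the same specimen.

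The cost is a wording change in two sections, made before the Phase 2 data are analysed. The data collected and the sample size of 246 stay as they are.
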